17. DATA ANALYSIS METHODS

[name], Statistical advisor, Royal Devon and Exeter hospital has been consulted.

Data collection and input will be carried out by the research team who will be employed by the RDEFT and will comply with local and national information governance standards. A password-protected Excel spreadsheet will be set up on a Trust computer in the Dermatology Department - also password protected. All paper and electronic data will be collected and stored in compliance with data protection guidelines, good clinical practice in research guidance and Trust clinical governance policy.

A feasibility study will provide an opportunity to assess the data to be collected and the choice of appropriate statistical tests for a future definitive trial. Data analysis will involve statistical methods appropriate to the data collected. The statistical analysis for the feasibility study will be descriptive for each group as hypothesis testing is not an aim of the feasibility study and it is likely to be underpowered for that anyway. Descriptive statistics of baseline characteristics will be compared between study groups to demonstrate the effectiveness of randomisation. Continuous outcome

Timing of Suture Removal to Reduce Scarring in Skin Surgery

data will be tested for normality using the Shapiro Wilks test. If the data are found to be normally distributed, central tendency will be expressed using means and dispersion using standard deviation. If the data prove not to be Gaussian, and cannot easily be transformed, they will be summarized using medians, interquartile ranges and ranges. Mean (or median) differences and the standard deviation of the differences will be used to inform sample size calculations for a definitive trial. Confidence intervals will be derived wherever possible. Categorical data will be summarized as proportions and percentages as appropriate with associated confidence intervals. No attempt will be made at this stage to make formal comparisons of outcome measures – this will be done in the eventual definitive study. Summaries of secondary outcome measures will also be produced in a similar manner to the above.

All data management will adhere to GDPR compliance. Statisticians will be blinded to allocation arms.

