14. AIMS AND OBJECTIVES

Aim:

To test the feasibility of conducting a definitive trial looking at outcomes for earlier removal of percutaneous sutures (7 days versus 10 days) for patients undergoing wide local excision and primary closure for treatment of skin cancers on the chest or back in dermatology.

Objectives:

1. To work out the standard deviation of the outcome measure (suture marks versus no suture marks) in order to estimate a sample size required for a properly powered RCT. (The incidence of 'suture marks' and the impact that these have on patients is currently unknown).
2. To provide some preliminary data on the incidence of wound complications and overall scar cosmesis in each group and ensure that this does not differ from expected:
 - a. *Overall cosmesis*
 - b. *Risk of post-operative bleeding*
 - c. *Risk of surgical site infection*
 - d. *Risk of wound dehiscence (opening up of scar)*
3. To assess the willingness of participants to be randomized.
4. To assess the willingness of clinicians to recruit patients.
5. To assess follow-up rates and adherence.
6. To assess the characteristics and ease of use of the proposed outcome measures including POSAS for scar assessment, a VAS, and patient reported outcome for complications including dehiscence and infection.
7. To gain feedback from patients at their three month follow up appointment on the patient pathway including the trial information leaflet and consent process.
8. To collect data on any additional costs that we may incur that have not been planned for, to inform costing for a future trial e.g. additional printing of PIS or consent forms or additional clinic booking slots
9. To use the gathered data to refine the design of the proposed RCT.

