18.4 Sample Size

As this is a feasibility study, it will not be powered to find significant differences between the groups. Instead it is an opportunity to test the feasibility of collecting the specified outcome data and describing it in terms of central tendency (mean, median) and dispersion (standard deviation or interquartile range as appropriate). A feasibility study provides an excellent opportunity to uncover problems ahead of time, minimizing the need to adapt procedures or to develop contingency plans at short notice when the larger study is being conducted. A simple method for choosing a sample size for a feasibility study that ensures the discovery of potential problems with high confidence is employed here [9]. The method is used to determine the necessary sample size so that a problem is likely to be observed at least once during the course of the feasibility study. The emphasis therefore is on “problem detection” and not on the estimation of the “problem frequency.” If the probability (p) of a problem arising is 0.05, then a sample size of 59 would be required to detect at least one instance of the problem. The formula for calculating this is approx. $3/p$ participants if one wants to be approximately 95% certain that the problem will manifest itself at least once during the feasibility study. We will aim for 30 analysable cases per group in the final dataset giving a total of 60 cases.

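### For the POSAS and VAS scores, a normality test decides whether an SD is reported, and the SD named for planning the RCT is not the one an unpaired two-group trial uses

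*Combined protocol and SAP*

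**What the plan says.** Section 17 first applies a gate: continuous outcome "data will be tested for normality using the Shapiro Wilks test". It then gives three routes.

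- **Test passed.** "If the data are found to be normally distributed, central tendency will be expressed using means and dispersion using standard deviation".
- **Test failed, transformation easy.** This route is only implied. The plan does not say what makes a transformation easy or on which scale the results are reported.
- **Test failed, no easy transformation.** "If the data prove not to be Gaussian, and cannot easily be transformed, they will be summarized using medians, interquartile ranges and ranges".

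The next sentence gives the use of these summaries: "Mean (or median) differences and the standard deviation of the differences will be used to inform sample size calculations for a definitive trial". It attaches no normality condition to the SD.

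Section 18.4 repeats the either/or, describing "dispersion (standard deviation or interquartile range as appropriate". Section 17 also says that "The statistical analysis for the feasibility study will be descriptive for each group". It gives no significance level for the test and does not say whether the test is run per arm or on both arms together.

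Objective 1 in section 14 is "To work out the standard deviation of the outcome measure". The same sentence defines that outcome as suture marks present or absent, and the data collection form (Appendix 8) records it as yes or no.

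**The concern.** The reporting rule and the planning rule do not fit together. A score that fails the test and resists transformation is reported without an SD. A score that is transformed would have an SD on, say, a log scale. The sentence that follows needs an SD in either case.

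The SD it names is also a problem. Patients are randomised to one of two parallel groups, and the scores are taken at one 3-month visit. No patient contributes a pair of values, so there is no set of differences whose SD can be taken. A two-group trial compared on means is sized from the within-group SD, which section 17 does not name.

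At stake is whether the study report gives a usable SD for the POSAS totals and the VAS, on the scale on which a later trial would be planned. Section 12 gives sample-size planning as a reason for the study, and objective 6 is to learn how these scales behave.

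**Working it through.** **1. The plan's own figure.** Section 18.4 wants about 95% certainty of seeing at least once a problem with probability 0.05. n = ln(0.05)/ln(0.95) = 58.40, rounded up to 59; the 3/p shortcut gives 60. Both agree with the plan, and neither depends on how scores are summarised.

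**2. Which outcomes the gate touches.** Section 17 summarises categorical data as proportions with confidence intervals, with no normality test. For a yes/no outcome SD = √(p(1−p)), for example √(0.2 × 0.8) = 0.40, so the gate cannot remove it. That leaves the POSAS totals (six items scored 1 to 10, so 6 to 60) and the VAS.

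**3. The SD of differences.** Let σ be the within-arm SD. Two literal readings are possible, and neither equals σ:
- The SD of the difference between one patient from each arm is √(σ² + σ²) = 1.41σ. Used as the SD in a two-group formula, it doubles n.
- The standard error of the difference in means at 30 per arm is σ√(1/30 + 1/30) = 0.26σ.

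**4. The usual planning input.** s_p = √{[(n₁−1)s₁² + (n₂−1)s₂²]/(n₁+n₂−2)}. With 60 analysable patients there are 58 degrees of freedom. The 95% CI multiplies s_p by √(58/χ²₀.₉₇₅) = 0.85 and √(58/χ²₀.₀₂₅) = 1.22. Since n scales with SD², the planned n is uncertain by factors of 0.85² = 0.72 to 1.22² = 1.49.

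**5. If only the IQR were available.** Suppose a later planner used IQR/1.349 for the SD. Assumptions: gamma-shaped scores, standardised effect 0.5, 90% power, two-sided 5%. With the true SD, n = 2(1.960 + 1.282)²/0.5² = 84.1, so 85 per arm.

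| Skewness | (IQR/1.349)/SD | n per arm | True power |
|---|---|---|---|
| 0.5 | 0.99 | 83 | 90% |
| 1 | 0.95 | 77 | 87% |
| 1.4 | 0.91 | 70 | 84% |
| 2 | 0.81 | 56 | 75% |

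**6. Different summaries in the two arms.** Assumptions: test run per arm, 5% level, 30 per arm, same gamma distribution in both arms, transformation ignored (6,000 simulated pairs).

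| Skewness | Rejected per arm | Arms disagree |
|---|---|---|
| 0 (normal) | 5% | 10% |
| 0.5 | 14% | 24% |
| 1 | 45% | 50% |
| 1.4 | 75% | 38% |
| 2 | 97% | 6% |

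The plan does not ignore transformation. A log cuts rejection from 45% to 16%, 75% to 27% and 97% to 47% at skewness 1, 1.4 and 2. For an assumed POSAS-like total (6 plus a gamma with shape 3 and scale 4, rounded), the log cuts it from 59% to about 5%. For an assumed VAS shape (beta 1.5, 4), a square root cuts it from 43% to about 3%.

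With r the chance that an arm ends in median/IQR, the arms split with probability 2r(1−r). For the last two shapes this falls from 2 × 0.59 × 0.41 = 48% to at most 2 × 0.05 × 0.95 = 10%, and from 2 × 0.43 × 0.57 = 49% to at most 2 × 0.03 × 0.97 = 6%. At skewness 2 a log still leaves 47% rejected, so the result depends on both the distribution and the transformation. No single rate belongs to this plan.

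A test on all 60 together would prevent disagreement between arms but not the missing SD: at skewness 1 it rejects 78% of the time.

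**The case against.** The strongest defence is that section 17 commits in its next sentence to using an SD whatever the test shows. The text is loose about what is tabulated, but nothing forbids computing an SD. The study is descriptive and makes no formal comparison. Section 19.7 keeps the data for 5 years, so an SD can be computed at any time. Median and IQR are conventional for skewed scores. All of this stands, and it limits the severity. It does not settle which SD is meant, on which scale, or whether it will appear in the report.

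Two stronger readings are tempting, and the documents support neither.

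- **A reader might infer that the rule removes the very number the study exists to obtain.** Objective 1 concerns suture marks present or absent. That outcome is outside the gate, and its variability follows from the proportion.
- **A reader might infer that the arms will receive different summaries about half the time.** That needs a per-arm test, a 5% level, a particular skewness and no transformation. The plan states none of the first three and provides for the fourth. The documents give no score data from which a distribution could be chosen.

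**Conclusion.** The point holds for the POSAS totals and the VAS, and it is minor. Section 17 is inconsistent about whether an SD on the original scale will be reported. The SD it names for planning has no clear meaning in an unpaired parallel-group design. Both faults can be read from the text and need no simulation.

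Disagreement between arms is a possibility that the plan leaves open, not a predicted outcome. The rates shown rest on an assumed 5% level, per-arm testing and assumed distributions. The power loss from an IQR-based SD (true power 90% down to 75%) is likewise illustrative and arises only if a planner has the published IQR alone. The sample size of 60 and the analysis of the yes/no suture-mark outcome are unaffected.

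**What to change.** In section 17:

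1. Remove the Shapiro-Wilk test as a gate. For each POSAS total and the VAS, report n, mean, SD, median, IQR and range per arm on the original scale. A transformed summary may be added but should not replace these.
2. Replace the SD of differences with the pooled within-arm SD and its 95% CI as the RCT planning input for continuous scores.
3. State that planning for the yes/no suture-mark outcome uses the per-arm proportions with the confidence intervals already specified.

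Align the either/or wording in section 18.4. The cost is a few lines of text and slightly wider tables. No extra data are needed, and the sample size does not change.

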12. THEORETICAL FRAMEWORK

We are interested to assess whether earlier suture removal reduces stitch marks in wounds where close approximation of wound edges can be achieved with dermal sutures. In doing so we hope to provide evidence that earlier suture removal reduces the risk of suture marks without increasing wound complications.

As the incidence of suture marks is currently uncertain and the impact that these have on the patient is unknown we intend to perform a feasibility study prior to conducting a randomized controlled trial. This study would give an indication as to the sample size required to power our RCT correctly. It will also provide an indication as to the ease of recruitment, patient participation, loss to follow-up, and complication rate. Furthermore, it will allow us to evaluate the use of our chosen assessment tools.

We have designed a single centre, randomized, blinded, parallel group feasibility study to assess viability of a randomized control trial (RCT) to answer this question.

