16. STUDY DESIGN

16.1 Study Setting, Population and Patient Identification

This is a **single centre prospective randomized assessor blinded parallel group feasibility study** that will be undertaken in the Royal Devon and Exeter Dermatology department, Heavitree Hospital. The initial skin cancer clinic, surgical procedure and follow-up will all be undertaken within the department.

Our patient population is all patients attending the dermatology department for wide local excision as part of their skin cancer treatment and primary closure of the subsequent wound.

Clinicians will identify potential participants during routine practice at their clinic visit. Patients who fulfil the entry criteria will be invited at that appointment to take part and given a patient information sheet (PIS). They will be offered and consented for a further telephone call to discuss the study further.

Timing of Suture Removal to Reduce Scarring in Skin Surgery

Alternatively, when patients are telephoned to inform them of the date of their surgery, they will be informed of the study then. If patients are interested in the study, they will be offered a further telephone appointment with a member of the research team to discuss the study further, answer any questions and gain verbal consent. The PIS can be emailed or posted to the patient at their request. All patients will be offered a telephone call between clinic visit and their date of surgery for any questions to be answered and verbal consent to be gained.

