16.6 Data Collection at 3 Month Follow Up

Patients will be booked in for a 3 month follow-up appointment, as per their standard care pathway. Data collection at 3 month follow up will include completing a patient and observer scar assessment scale (POSAS) with regards to overall scar cosmesis, and also a visual analogue scale (VAS) in relation to suture marks specifically. We have chosen these tools as they are validated, well known scales to characterise scars subjectively and objectively [10].

The patient will be asked about any post-operative complications that were not detected at suture removal including wound infection, dehiscence, and significant post-operative bleeding (defined as bleeding requiring assessment by a healthcare professional). Assessment will be carried out by a member of the research team who will be blinded to trial allocation.

Photographs of the scar will be taken at the follow-up visit using the departmental camera to allow review of scar assessment at a later date if required. This will be directly uploaded onto their electronic patient record in line with Trust policy. Patients will be verbally consented for this at time of follow up, as per usual practice.

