19.7 Data Protection and Confidentiality

The patients will be recruited to the trial and all data will be stored anonymously against a participant number. Only the clinical team will have access to the single table correlating patient name and participant number. This information will not be shared. All clinical and routine data will be collected and placed in a database by the clinical team preserving anonymity throughout the trial. It has been considered that the feasibility trial may begin to demonstrate clear advantages of one technique over the other. However, with the patient numbers involved, it seems unlikely that differences in the technique will be observed at levels that are statistically significant.

Data will be stored for 5 years then destroyed appropriately.

All paper and electronic data will be collected and stored in compliance with data protection guidelines, good clinical practice in research guidance and Trust clinical governance policy.

Please see 'Data Analysis Methods' for further information.

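### The rule for sizing the definitive trial names a standard deviation that a parallel-group design does not produce, and an observed difference too imprecise at about 30 per arm to be the target effect

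*Combined protocol and SAP*

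**What the plan says.** Sizing a later trial is a declared purpose of this study. Section 12 states: "This study would give an indication as to the sample size required to power our RCT correctly". Objective 1 in section 14 reads: "To work out the standard deviation of the outcome measure (suture marks versus no suture marks) in order to estimate a sample size".

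Section 17 gives the only rule that names inputs for that calculation: "Mean (or median) differences and the standard deviation of the differences will be used to inform sample size calculations for a definitive trial". It comes directly after the rules for continuous outcomes, including this one: "If the data prove not to be Gaussian, and cannot easily be transformed, they will be summarized using medians, interquartile ranges and ranges". Proportions with confidence intervals are planned for categorical data two sentences later, but they are not linked to the sizing step.

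Section 16.1 describes a "single centre prospective randomized assessor blinded parallel group feasibility study". Under section 16.6 the scar is scored once, at 3 months, with POSAS and "also a visual analogue scale (VAS) in relation to suture marks specifically". The data collection form (Appendix 8) records visible stitch marks as yes or no.

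On precision, section 18.4 says of the study that "it will not be powered to find significant differences between the groups", and section 19.7 adds that "it seems unlikely that differences in the technique will be observed at levels that are statistically significant". No section gives a clinically important difference for any outcome, or the significance level and power of the definitive trial.

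**The concern.** The sizing sentence names two inputs, and neither suits the design.

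- **The SD.** An SD of differences belongs to paired or before-and-after data. Here each patient is in one arm, there is no baseline scar score, and scars are scored once. There is no patient-level difference whose SD could be taken.
- **The difference.** A between-arm difference from about 30 patients per arm is too imprecise to stand in for the effect the definitive trial should detect. The plan itself says the study is not powered for differences.

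Two smaller gaps sit beside these. For the yes/no outcome, objective 1 asks for an SD, and the sizing sentence does not mention the proportions that would drive that calculation. For continuous scores that are not normal and not easily transformed, the planned summary leaves out the SD that the next sentence relies on.

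At stake is a definitive trial that is far too small or far too large, if the rule is applied as written.

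**Working it through.** **1. The plan's own figure.** Section 18.4 wants about 95% certainty of seeing at least once a problem with probability 0.05. n = ln(0.05)/ln(0.95) = 58.4, rounded up to 59; the approximation 3/p gives 60. The figure reproduces. It was chosen to detect problems, so it does not bear on how precisely a difference is estimated.

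**2. Inputs.** From the documents: parallel arms, 30 analysable per arm (18.4), one assessment at 3 months (16.6), a yes/no suture-mark outcome (Appendix 8). Assumed, because the documents give none: two-sided 5%, 80% power and the true effects below.

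**3. Which SD.** For two independent means, n per arm = 2(1.960 + 0.842)² × SD²/Δ², where SD is the within-arm SD and Δ the target difference. With d = Δ/SD this is 15.70/d². At d = 0.5, n = 15.70/0.25 = 62.8, so 63 per arm. No SD of paired differences enters.

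**4. Precision of the observed difference.** Standard error = SD × √(2/30) = 0.258 SD. With t(58) = 2.002 the 95% half-width is 0.52 SD. An observed 0.5 SD therefore has a 95% interval of −0.02 to 1.02 SD.

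**5. Sizing from the observed difference.** Put the observed difference divided by the pooled SD into 15.70/d². Its distribution is noncentral t on 58 degrees of freedom, scaled by √(2/30). An observed difference of zero or in the wrong direction counts as no benefit.

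| True effect | n per arm needed | Quartiles of implied n | Under half | Over twice, or no benefit |
|---|---|---|---|---|
| 0.3 SD | 174.4 | 68 and 985 | 32% | 37% |
| 0.5 SD | 62.8 | 34 and 148 | 22% | 28% |
| 0.8 SD | 24.5 | 16 and 40 | 12% | 18% |

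The problem shrinks as the true effect grows but is still there at 0.8 SD.

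**6. Precision of the pooled SD.** On 58 degrees of freedom its 95% interval is 0.85 to 1.22 times the estimate. For a fixed target difference, n scales with SD², a factor of 0.72 to 1.49. For the 62.8 above that is 62.8 × 0.72 = 45 to 62.8 × 1.49 = 94 per arm: wide, but usable.

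**7. The yes/no outcome.** If a proportion p has suture marks, the SD is √(p(1 − p)), so it adds nothing to p. The same weakness would arise if an observed difference in proportions were used. With n per arm = (1.960 + 0.842)²[p₁(1 − p₁) + p₂(1 − p₂)]/(p₁ − p₂)² and assumed rates of 50% and 30%, n = 7.85 × (0.25 + 0.21)/0.04 = 90. Enumerating all 31 × 31 outcomes at 30 per arm gives quartiles of 40 and 217; 26% fall under half, and 34% go over twice or show no benefit. This is an illustration only: the plan does not say it would size the suture-mark outcome in this way.

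**8. Precision of a single-arm proportion.** An assumed 30% (9 of 30) has a Wilson 95% interval of about 17% to 48%.

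**The case against.** The best defence is that the sentence is loosely worded and not a binding rule. The differences are only to inform the calculation, section 12 promises only an indication, confidence intervals are planned wherever possible, and a statistical advisor was consulted. The intended SD is probably the within-arm one, which section 17 already reports by group when data are normal. Nothing in the present study is harmed: the sample of 60, data capture and descriptive analysis are untouched, and the definitive trial is itself conditional.

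Much of this stands, and it limits the consequence. It does not rescue the sentence. No other input is named and no important difference appears anywhere, so a reader who follows section 17 has only these two quantities. A confidence interval shows the imprecision of the observed difference but does not make it a sound target.

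Four stronger readings are tempting, and the documents do not support them.

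- *The definitive trial would be twice too large.* The SD of differences between unrelated patients is √2 times the within-arm SD, and entering it in a two-arm formula would double n. That needs an arbitrary pairing of patients, which nothing in the plan suggests.
- *Sizing for suture marks is invalid.* The quoted sentence concerns the continuous scales. The SD in objective 1 is redundant with the proportion, not wrong.
- *The omitted SD is lost.* Section 17 has the individual values entered in a study spreadsheet, and section 19.7 keeps them for 5 years, so the SD can still be calculated when medians are reported.
- *Blinding the statistician blocks the calculation.* Section 16.4 maintains concealment only until trial completion, and the pooled SD needs only masked group labels.

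The remark in section 19.7 on statistical significance was made about an advantage emerging during the study. It supports low precision; it does not contradict the sizing rule.

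**Conclusion.** The point holds as a correction to a stated rule. The SD named in section 17 does not exist in this design, and the observed difference at about 30 per arm should not be the target effect. The size of the second problem rests on assumed effects, 80% power, two-sided 5%, and use of the point estimate without further judgement; a more cautious use would do less damage. The 30 per arm is itself a target, so precision would be lower with fewer analysable patients.

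Objective 1 and the sizing sentence should also be brought into line, because neither ties the calculation to the proportion with suture marks. The impact is minor to moderate. The consequence falls on a later trial, and it can be recovered from the retained data. The change is still worth making now, because the target difference is best set before the observed one is seen.

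**What to change.** 1. Reword objective 1 (section 14): *estimate the proportion with suture marks in each arm, with 95% CI, to inform the sample size of the RCT*.
2. Replace the sizing sentence in section 17: *The definitive trial will be sized on a prespecified clinically important difference, not the observed difference, using the 10-day-arm proportion with suture marks across its 95% CI and, for POSAS and VAS, the pooled within-arm SD with its 95% CI, calculated whatever the normality result.*

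The cost is wording in two sections. No new data are needed and the sample of 60 does not change. The investigators must choose the important difference, since the documents give none and this study cannot supply it. The 10-day proportion will be imprecise, as the interval of about 17% to 48% shows, so the size of the definitive trial should be presented as a range.
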